- Willing to come to the hyperbaric facility on successive days (one control session and one hyperbaric treatment), spending approximately 3 hours in the facility on each day of testing
- Willing to undergo multiple fingersticks on the days of testing
- Willing to have a peripheral intravenous catheter placed for blood sampling
- Willing to perform four daily fingerstick blood glucose checks throughout the study period

Exclusion Criteria

- Contraindication to HBO₂ as determined by the study investigator (*e.g.*, pregnancy)
- Previous treatment with HBO₂ within 30 days of enrollment

December 4, 2019

- Current use of CGM is not an exclusion, but participants must use study equipment during the study
- Current use of an insulin pump
- Known allergy to medical-grade adhesives
- Extensive skin changes/disease that preclude wearing the sensor on normal skin (e.g. extensive psoriasis, recent burns or severe sunburn, extensive eczema, extensive scarring, extensive tattoos, dermatitis herpetiformis)

Control Protocol (Figure 3)

Because the effects of HBO₂ may extend longer than one day, participants will first be exposed to a 2-hour control period where they will simulate an HBO₂ exposure. Patients must be NPO after midnight of the day prior to the control study period. Participants in a control session will sit quietly (as they would in the hyperbaric chamber) and will not be allowed to consume carbohydrates unless directed to by the hyperbaric department hypoglycemia protocol. The timing of the blood draws (Figure 5) will be parallel to that of the HBO₂ exposure.

[figure not shown]
Figure 3. Control Testing Protocol

Hyperbaric Oxygen Therapy (Figure 4)

The day after the control study period, participants will undergo a standard HBO₂ treatment breathing 100% oxygen at 2.4 ATA with 3 x 30 min O₂ periods and 5 min air-breaks between O₂ periods. Patients must be NPO after midnight of the day prior to the HBO₂ period. Participants will not be allowed to consume carbohydrates during the treatment unless directed to by the hyperbaric department hypoglycemia protocol.

Figure 4. HBO₂ Testing Protocol

Modification of hypoglycemia medication regimen

Because participants are being asked to remain NPO after midnight, they will be asked to modify their normal hypoglycemic medications as follows:

- Oral hypoglycemic medications should be held until after they eat their first meal of the day

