- Patients with meal-time doses of insulin should hold their meal-time boluses until they eat their first meal of the day
- Patients who require a correction dose of insulin the morning of study session (control of HBO₂) because of a blood glucose >250 mg/dL should take their normal dose of insulin and document it in their medication log
- Patients who use long-acting insulin should modify their doses as follows
 - Patients who are on BID long-acting insulin to take their normal dose in the morning, but 2/3 of their dose the night before
 - Patients who are on night-time long-acting insulin to take 2/3 their normal dose the night before
 - Patients who are on morning long-acting insulin to take 2/3 of their normal dose in the morning

Study investigators will review insulin doses and provide additional instructions for adjustment if needed for safety.

Modification of the Hyperbaric Department Glucose Protocol

The hyperbaric department currently follows a protocol to provide supplemental carbohydrates to patients with a pre-HBO₂ BG <100 mg/dL whether they are

December 4, 2019

symptomatic or not. We will be following the hyperbaric department protocol and obtaining pre-HBO₂ fingerstick blood sugars, but we will not provide mandatory supplemental carbohydrate for BG <100 mg/dL unless participants complain of symptoms they associate with hypoglycemia. If participants are documented to have hypoglycemia – defined by the American Diabetes Association (ADA) as a BG ≤ 70 mg/dL¹⁰ – before or during study periods, we will institute the hyperbaric department’s hypoglycemia protocol and provide 15 grams of supplemental carbohydrate. Hypoglycemia risk to the patient is mitigated because we will be able to monitor blood sugar in real time using CGM, however clinical decisions will be made using the fingerstick GDH-based POC glucometer.

Transcutaneous Oxygen Monitoring during HBO₂ exposures

We will obtain concurrent transcutaneous oximetry measurements (TCOM) using a Clarke electrode (Radiometer America, Brea, CA) attached no farther than 3 cm from the commercial CGM on the abdomen to measure tissue oxygenation in the region of the CGM only during HBO₂ exposure. The TCOM value closest to the time of each blood draw will be used for analysis. The average pre-HBO₂ TCOM measurements will be used as a surrogate for the control day TCOM.

Hemoglobin A1c

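### Session type cannot be separated from study day: HBO₂ follows two reduced long-acting insulin doses and control follows one, yet Endpoints 2 and 3 are read as HBO₂ effects

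*Combined protocol and SAP*

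**What the plan says.** **Order and spacing.** The Control Protocol section puts control first for everyone: "Because the effects of HBO₂ may extend longer than one day, participants will first be exposed" to the control period. The Hyperbaric Oxygen Therapy section adds: "The day after the control study period, participants will undergo a standard HBO₂ treatment". Figures 1 and 2 place control on Day 3 and HBO₂ on Day 4, and the inclusion criteria require adjacent days: "Willing to come to the hyperbaric facility on successive days (one control session and one hyperbaric treatment".

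**Medication.** Fasting from midnight is required before both sessions. The section headed Modification of hypoglycemia medication regimen makes that fast the trigger for its changes: "Because participants are being asked to remain NPO after midnight, they will be asked to modify their normal hypoglycemic medications as follows". Three long-acting regimens are covered:
- Night-time: "Patients who are on night-time long-acting insulin to take 2/3 their normal dose the night before".
- Morning: "Patients who are on morning long-acting insulin to take 2/3 of their normal dose in the morning".
- Twice daily: "Patients who are on BID long-acting insulin to take their normal dose in the morning, but 2/3 of their dose the night before".

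Oral agents and meal-time insulin are only delayed, with no two-thirds reduction. A morning glucose above 250 mg/dL calls for a correction dose, to be entered in the medication log. The next section provides 15 g of carbohydrate at 70 mg/dL or below.

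**Analysis.** Endpoint 2 compares glucose at timepoints 1-3 with timepoints 10-12 in a linear mixed model. Its main effect is the pre-to-post difference by session type. Endpoint 3 compares control glucagon with glucagon before, during and after HBO₂, with no baseline subtraction specified. Neither endpoint mentions a day or period effect. The log described under Ancillary Data collection has no stated use in either analysis.

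**The concern.** Using each participant as their own control removes differences between people. It does not remove differences between a person's two days. Here the days differ in a known way: long-acting insulin users have had one more reduced dose by the HBO₂ session than by the control session. Anything this does to glucose or glucagon coincides with HBO₂ in every such participant.

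At stake is what Endpoints 2 and 3 can conclude. The plan intends to attribute the session contrast to HBO₂. As designed, that contrast is HBO₂ plus whatever changed between Day 3 and Day 4, and nothing in the Analysis section tells the reader so.

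**Working it through.** The plan gives no effect size or sample size for Endpoint 2 or 3 (its 18 patients relate to Endpoint 1), so there is no plan figure to reproduce.

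**1. Reduced doses taken by the start of each session** (default instructions applied to both sessions)

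| Regimen | Before control (Day 3) | Before HBO₂ (Day 4) |
|---|---|---|
| Night-time | 1 | 2 |
| Morning | 1 | 2 |
| Twice daily | 1 (evening) | 2 (evenings, with a normal morning dose between) |
| No long-acting insulin | 0 | 0 |

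**2. Can the model separate day from session?** Write the fixed effects as intercept, session, post, session×post, day and day×post. With the order fixed, day equals session in every row, so the last two columns duplicate the session and session×post columns. The design has rank 4 with 6 columns. No covariate for day can be estimated alongside session.

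**3. What passes into Endpoint 2.** Let E be the true HBO₂ effect on the pre-to-post change, d the change on the control day, L a Day 4 shift in starting level and S a Day 4 difference in within-session trajectory.
- Control change: d.
- HBO₂ change: (L + d + S + E) − L = d + S + E.
- Contrast: E + S.

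L cancels and S does not. If a fraction f of participants is affected, the contrast is E + f×S. With E = 0 and everyone affected, L = 20 mg/dL alone gives a bias of 0, and S = 10 mg/dL gives 10 with or without that L. At f = 0.75 and 0.5, S = 10 gives 7.5 and 5.

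S can arise from a different fasting drift. It can also arise from L itself, because a shifted level changes how often the 250 mg/dL correction dose or the 70 mg/dL carbohydrate rule is triggered.

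**4. Illustrative size.** Times come from the blood sampling schedule.
- Mean pre time: (−30 − 15 + 0)/3 = −15 min.
- Mean post time: (115 + 130 + 145)/3 = 130 min.
- Gap: 145 min = 145/60 = 2.42 h.

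| Assumed drift difference (mg/dL per hour) | All affected: drift × 2.42 h (mg/dL) | 50% affected (mg/dL) |
|---|---|---|
| 2 | 4.8 | 2.4 |
| 5 | 12.1 | 6.0 |
| 10 | 24.2 | 12.1 |

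The drift rates are assumptions; the documents give none. For scale, the Background reports a pre-to-post CGM change of 4.12 mg/dL in healthy volunteers. A drift difference of 4.12/2.42 = 1.7 mg/dL per hour in all participants would equal it.

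**5. Endpoint 3.** Levels are compared directly, so a Day 4 shift L in glucagon enters in full, as f×L. Subtracting or adjusting for Timepoint 1 deals with that shift. It does not deal with a trajectory difference. Timepoint 1 is the only pre-session glucagon sample, so no pre-session glucagon slope can be fitted.

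**6. How good is a pre-session glucose slope?** For three samples at 15-minute spacing, the sum of squared time deviations is 2 × 0.25² = 0.125 h². The standard error of the slope is SD/√0.125 = 2.83 × SD per hour. At an assumed per-sample SD of 2 to 3 mg/dL, that is 5.7 to 8.5 mg/dL per hour per participant, similar to the drifts in step 4.

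**The case against.** Control first is a reasoned choice: it keeps any lasting HBO₂ effect out of the control session. The Endpoint 2 contrast is a difference of changes, so the obvious worry, a higher starting glucose on Day 4, drops out. Both points stand. Neither removes the trajectory route in Endpoint 2 or the level route in Endpoint 3.

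The mg/dL figures are assumed drift rates multiplied by a time interval, and the larger set requires every participant to be affected. That also stands, so they are illustrations and not estimates.

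The remedies have limits. The pre-session slope is noisy and shares its samples with the pre-session mean. Splitting 24 people by long-acting insulin use gives small groups that may largely follow diabetes type. These objections argue for sensitivity and descriptive status, not for omitting the analyses.

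Three stronger readings are tempting and unsupported:
- A reader might infer that the bias hides a fall in glucose, since less basal insulin pushes glucose up. But if Day 4 glucose is higher, more correction doses may be taken, and these push it down. The documents do not settle the net sign.
- A reader might infer that every type 1 participant is exposed, because pump users are excluded. The documents do not say what the remaining participants use; the reductions are conditional on long-acting insulin.
- A reader might infer that the insulin deficit is doubled. Two against one is a count of doses. No duration of action is given, twice-daily users take a normal dose in between, and investigators may adjust individual instructions.

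**Conclusion.** The concern holds in a limited form. Session type is fully aliased with day, and under every long-acting regimen HBO₂ follows two reduced doses and control one. Endpoint 2 is protected against a pure level shift but not against a day-related difference in trajectory. Endpoint 3, as written, is protected against neither.

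The size and sign of the distortion cannot be obtained from the documents. The illustrative 5 to 24 mg/dL (2.4 to 12.1 at 50% affected) rests entirely on assumed drift differences of 2 to 10 mg/dL per hour. The dose asymmetry applies only to long-acting insulin users, whose number is not stated. The aliasing applies to everyone. This does not invalidate the trial, but it limits what can be attributed to HBO₂, and the plan should say so.

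**What to change.** Change the Analysis section only; dosing and the visit schedule stay as they are.

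1. State that the Endpoint 2 and 3 contrasts estimate session plus day, and word the conclusions accordingly.
2. For Endpoint 3, analyse change from each session's own Timepoint 1 glucagon, or adjust for it.
3. For Endpoint 2, pre-specify two sensitivity analyses. One adjusts for the pre-session trend over timepoints 1-3, with a note that a three-point slope is imprecise. The other uses the medication log to account for correction insulin, together with any carbohydrate given in the session.
4. Report the session effect separately for participants on and not on long-acting insulin, as a descriptive check. The second group has no dose asymmetry, though it remains subject to any other day effect.

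The cost is plan wording and some analysis time. The glucose, glucagon and log data are already to be collected; the plan should confirm that in-session carbohydrate and long-acting insulin use are recorded. The downside is imprecise sensitivity estimates in 24 people and a more cautious conclusion.

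The stated carryover reason supports control first but does not by itself require the very next day. Whether successive days are needed is for the sponsor to consider.

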- Use of CGM devices does not present a potential for serious risk to the health, safety or welfare of a subject.

There is a very low risk of developing a local skin infection at the site of the sensor placement and a very low risk of sensor breakage. The participant will be instructed to notify study staff if they develop swelling, redness, or pain at the sensor insertion site.

Adverse Events

We will catalog adverse events associated with HBO₂ (e.g., otic/sinus barotrauma, O₂ toxicity, confinement anxiety) or severe hypoglycemia (BG < 70 mg/dL) associated with HBO₂. We will report any complications related to the insertion of the CGM or fingersticks related to home glucose testing. Asymptomatic patients with a BG <100

December 4, 2019

mg/dL will not be considered an adverse outcome associated with HBO₂ but will be counted for analysis.

Analysis

Endpoint 1

In order to determine the accuracy of the G6 CGM in patients with diabetes who are receiving HBO₂, we will compare CGM values to laboratory results in the pre-HBO₂ NBAir (1-3), HBO₂ (4-9), and post-HBO₂ NBAir (10-12) phases. We will compare the mean absolute relative difference (MARD), which is listed at 9.9% in the Dexcom G6 user guide and has a standard deviation of 7.99 mg/dL. If we are trying to detect a difference of 5 percentage points in MARD (9.9% in room air up to 14.9% in HBO₂) with a standard deviation of 8 mg/dL, alpha level ($p < 0.05$), and a power of 0.80, we will require a minimum sample size of 18 patients.

Endpoint 2

We will compare CGM and venous blood glucose readings before (1-3), and after (10-12) each study session and use this to determine if there is any effect of session type (HBO₂ vs control) on BG. Each individual will serve as their own control, which will improve the study's power. We will determine if the BG changes observed during HBO₂ sessions are greater than those observed when the participants are sitting quietly outside the chamber during the control sessions. Linear mixed effects regression (LMER) analyses will be used to account for the clustering of data within an individual while also allowing for the main effect (difference in pre- vs. post- by session type) to be determined.

Endpoint 3

We will evaluate whether a single HBO₂ treatment affects glucagon levels by comparing control glucagon levels with the pre-, intra-, and post-HBO₂ glucagon levels.

December 4, 2019

Estimated time to conduct study

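### The hypoglycemia adverse-event rule contradicts itself for asymptomatic readings below 70 mg/dL, and it cannot list lows from the control session

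*Combined protocol and SAP*

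**What the plan says.** Four parts of the combined protocol and SAP bear on this point.

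- **Adverse Events.** Among the events to be catalogued is "severe hypoglycemia (BG < 70 mg/dL) associated with HBO₂". The paragraph closes by saying that asymptomatic patients with a BG below 100 "mg/dL will not be considered an adverse outcome associated with HBO₂ but will be counted for analysis".
- **Modification of the Hyperbaric Department Glucose Protocol.** Hypoglycemia is "defined by the American Diabetes Association (ADA) as a BG ≤ 70 mg/dL". It carries no severity grade and is treated with 15 g of carbohydrate before or during study periods. The department's usual carbohydrate for a pre-HBO₂ reading below 100 is waived unless the participant has symptoms. On the measuring device, "clinical decisions will be made using the fingerstick GDH-based POC glucometer".
- **Control Protocol.** Participants fast from midnight, sit quietly "and will not be allowed to consume carbohydrates unless directed to by the hyperbaric department hypoglycemia protocol". On sampling, "The timing of the blood draws (Figure 5) will be parallel to that of the HBO₂ exposure". The order of sessions is fixed: "Because the effects of HBO₂ may extend longer than one day, participants will first be exposed to a 2-hour control period", and HBO₂ follows the next day.
- **Exclusion Criteria.** One exclusion is "Previous treatment with HBO₂ within 30 days of enrollment".

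**The concern.** The Background gives two accounts of low glucose after HBO₂: an effect of the treatment, or a decline already under way when the patient enters the chamber. The control day exists to separate them. Fasting participants, some of whom will have taken long-acting insulin, may have lows on either day, and the Control Protocol provides for that. A catalogue confined to HBO₂-associated lows would show one day only. A reader of the safety report could not tell whether such lows were more frequent than on a fasting day outside the chamber.

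There is also a coding problem. Two people applying the Adverse Events paragraph to the same asymptomatic reading below 70 could reach opposite answers, and each could cite the text. If that is settled only once results are known, the person deciding will know the session and the reading.

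**Working it through.** No sample-size or power figure is involved, so the check is to apply the written rules to test readings and then to each session.

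**Step 1: test readings.** Take an asymptomatic participant during HBO₂.

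| BG (mg/dL) | Hypoglycemia, treated (≤70) | Catalogued as severe (<70) | Exempt as asymptomatic (<100) |
|---|---|---|---|
| 54 | yes | yes | yes |
| 69 | yes | yes | yes |
| 70 | yes | no | yes |
| 71 | no | no | yes |
| 99 | no | no | yes |
| 100 | no | no | no |

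- Below 70, the third and fourth columns conflict for every asymptomatic value.
- At exactly 70, the participant is treated for hypoglycemia but no event is catalogued. This is the only value at which the two cut-offs differ.
- From 71 to 99 the rules agree.
- The severe label sits on almost the same threshold that the glucose-management section calls hypoglycemia without qualification.

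**Step 2: can a control-session low be catalogued?** The condition is association with HBO₂. The control session is on Day 3 and the HBO₂ session on Day 4 (Figure 1), so no study HBO₂ has yet been given. Treatment in the 30 days before enrollment is excluded. A control-session low therefore cannot meet the condition.

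**Step 3: which HBO₂ lows count as associated?** The plan does not say. A low at timepoints 1-3 on the HBO₂ day comes before compression. At the other end, the Control Protocol allows that effects may last longer than a day, and participants take at least four home fingersticks daily through the follow-up days. A later low at home could therefore also be called associated.

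**Step 4: do the readings exist?** Yes. Figure 1 shows 12 point-of-care fingerstick measurements and 12 venous glucose measurements in each session. The budget agrees: 12 + 12 = 24 laboratory glucose tests per subject, and 24 subjects × 24 = 576, the quantity listed.

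**Step 5: does another analysis supply the comparison?** Endpoint 1 concerns CGM accuracy and Endpoint 3 concerns glucagon. Endpoint 2 compares the change in glucose from before to after by session type. None compares counts of lows or of carbohydrate given.

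**The case against.** The strongest reply is that little depends on this. Participants are treated at 70 or below in either session, the readings are collected, and Endpoint 2 already tests the rival explanation on glucose change with each person as their own control. All of that stands. It limits the point to the safety report.

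On the self-contradiction, the figure of 100 has a visible source: it is the department's usual carbohydrate threshold, which the study waives. The authors probably meant the band from 70 to 100, and the more specific rule for values below 70 can be read as taking precedence. Exempted patients are also still to be counted for analysis. The intent is plausible, but the text does not state it, and the promise to count names neither a session nor a table.

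The cut-off difference and the severe label are close to editorial. The documents contain no severity scale that the label breaches, and no action depends on it. Both are worth correcting along with the rest but would not justify a comment alone.

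On the device, the laboratory hexokinase result is the plan's reference for glucose accuracy, so using the GDH fingerstick to classify events is a choice. The reason for it is that the fingerstick governs clinical decisions, so the event list would match the carbohydrate given.

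**Conclusion.** The point holds for the hypoglycemia safety report. As written, the rule gives contradictory coding for every asymptomatic reading below 70 on HBO₂, and it leaves the report without a control-session comparator in a study where each person is their own control. This should be corrected, but it does not threaten the trial.

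Three stronger conclusions might be inferred, and the documents support none of them.

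- *The trial cannot separate an HBO₂ effect from a fasting decline.* Endpoint 2 addresses that on glucose change and is untouched.
- *Participants are at greater risk.* The treatment rule covers both sessions and does not depend on the adverse-event wording.
- *The size can be expressed as a share of scheduled readings.* Such a share would depend on the reader's own meaning for associated, would omit home fingersticks after HBO₂, and would count readings rather than events. No hypoglycemia rate is given, so no number of affected events can be stated.

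The verdict assumes that the Adverse Events paragraph is the whole catalogue rule. The department's hypoglycemia protocol is cited but not reproduced, and nothing in the plan says that it provides a control-session listing.

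**What to change.** 1. Define hypoglycemia as BG ≤70 mg/dL throughout, and drop the word severe for this threshold.
2. Limit the asymptomatic exemption to BG above 70 and below 100 mg/dL.
3. State that events are classified by the GDH fingerstick, as for clinical decisions.
4. Tabulate lows and rescue carbohydrate by the same rule in the control and HBO₂ sessions, by phase (timepoints 1-3, 4-9 and 10-12). Showing the phase removes the need to judge association for lows within a session. Keep the table descriptive, with no formal test; its layout is a matter of preference.
5. Note beside the table that control always precedes HBO₂ by a day, so a difference between sessions cannot be attributed to HBO₂ alone.

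The cost is a few lines of protocol wording and one table built from readings already scheduled. No samples are added, and the endpoints and sample size do not change. The downside is a longer event list, since readings of exactly 70, asymptomatic lows and control-session lows would all appear.
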